## 8. STATISTICAL AND QUANTITATIVE ANALYSES

### 8.1 Statistical Methods

The primary endpoint will be the  $\geq$  VGPR response proportion as best response within the first 8 cycles of treatment. Based on historical data, the  $\geq$  VGPR response proportion is approximately 9%; therefore, the target  $\geq$  VGPR response proportion will be  $\geq$  25%.

This exact single-stage design yields a  $\geq$  0.80 probability of a positive result if the true  $\geq$  VGPR response proportion is  $\geq$  25%. It yields a  $\geq$  0.95 probability of a negative result if the true  $\geq$  VGPR response proportion is  $\leq$  9%. A 95% confidence interval constructed around the expected  $\geq$  VGPR response proportion of 25% can be estimated to be within  $\pm$  17.9% of the observed  $\geq$  VGPR response proportion.

Analysis Plan for Endpoints:

Primary Endpoint:

The primary endpoint is the  $\geq$  VGPR response proportion as best response within the first 8 cycles of treatment; A 95% confidence interval will be estimated for the  $\geq$  VGPR response proportion via binomial proportions.

Secondary endpoints:

Secondary endpoints include median PFS, OS, time to response and progression, DoR, TTNT, ORR, VGPR rate, CR or better rate, improvement in response rate during maintenance therapy and MRD negativity rate. Median PFS/OS, including survival curves, will be estimated using Kaplan-Meier methodology. Greenwood's formula will be used to calculate 95% confidence intervals for the Kaplan-Meier survival estimates.

All analyses will be performed in SAS Version 9.4 (SAS Institute, Inc., Cary, North Carolina) and Stata Version 15.0 (StataCorp, College Station, Texas).

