## Protocol Summary

Full Title:	A PHASE II STUDY OF DARATUMUMAB, CLARITHROMYCIN, POMALIDOMIDE AND DEXAMETHASONE (D-ClaPd) IN MULTIPLE MYELOMA PATIENTS PREVIOUSLY EXPOSED TO DARATUMUMAB
Short Title:	D-ClaPd IN REL/REF MULTIPLE MYELOMA
Clinical Phase:	2
Principal Investigator:	[name] [name]
Study Description:	This single-arm phase 2 study will test the hypothesis that in patients with previous daratumumab exposure, daratumumab in combination with ClaPd will yield higher $\geq$ VGPR rates in historical pomalidomide/dexamethasone.
Sample Size:	N= 40
Enrollment:	This study will enroll 40 subjects and screen up to 44 subjects.
Study Population:	Patients will be over 18 years of age with relapsed/refractory multiple myeloma. Patients who have received 1 or more prior lines of therapy which must include daratumumab and may include ASCT are eligible. The patient must have received both an IMiD and PI in prior lines. Prior pomalidomide exposure in 1 or more previous lines of therapy allowed if PR or better achieved. No disease progression may have occurred within 60 days of receiving pomalidomide. Patient may be daratumumab refractory (i.e less than a PR) achieved on prior daratumumab-based therapy or have exhibited progression within 60 days of receiving daratumumab.
Study Design:	This is a single-center single-arm phase 2 study in which 40 patients will receive daratumumab in combination with clarithromycin/pomalidomide/dexamethasone until PD or unacceptable toxicity, whichever comes first. Patients will be treated for 8 cycles of therapy with continuation of maintenance daratumumab/pomalidomide if evidence of PR or better.

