## 4.2 Number of Patients

Approximately 40 patients will be enrolled and treated on study.

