#### 8.1.1 Determination of Sample Size

The sample size computations were performed assuming a 5% level of significance and 80% power. The new regimen will be declared effective and worthy of further testing if 8 or more patients have  $\geq$  VGPR among the 40 patients entered into the cohort.

Sample size recommendations for the current design are determined according to A'Hern's exact single-stage phase II design (A'Hern, RP, 2001). We project a  $\geq$  VGPR response proportion of 9%, below which the regimen will be unacceptable, and a  $\geq$  VGPR response proportion of 25%, above which the regimen will be considered worthy of further exploration. The null hypothesis that the  $\geq$  VGPR response proportion is less than or equal to 9% will be tested against the alternative hypothesis that the  $\geq$  VGPR response proportion is greater than or equal to 25%.

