##### Response

Parameters assessed will include stringent complete response (sCR), complete response (CR), very good partial response (VGPR), partial response (PR), and stable disease (SD) per standard IMWG response criteria. In addition, overall response rate (defined as greater than or equal to PR across all cycles of treatment), response duration, time-to-response (TTR), MRD negativity rate and improvement in response during maintenance therapy will be assessed.

Best overall response categories will be tabulated and overall for CR, VGPR, PR, SD, progressive disease, and relapse. A two-sided 95% exact binominal CI will be calculated for each category. The response rate (responses  $\geq$  PR) will also be tabulated. Time-to-event analyses will be done using Kaplan- Meier analyses and will include time to response, duration of response, PFS, and OS, as data allow. If there is not enough data to apply the Kaplan-Meier test, the data will be summarized by descriptive statistics.

Time to response (for responders only) will be calculated as the time from the date of first study treatment dosing to the first date of documented response (PR or better) and will be summarized by descriptive statistics.

Duration of response (for responders only) is defined as the time from the earliest date of documented response (PR or better) to the earliest date when disease progression was confirmed. Patients who are non-responders will be excluded from this analysis. Detailed censoring rules for duration of response will be specified in the SAP.

PFS will be calculated as the time from the initial administration of Daratumumab, Clarithromycin, Pomalidomide, and Dexamethasone until documented disease progression, as determined using standard response criteria, or death from any cause, whichever occurs first. Kaplan-Meier methods will be used to estimate PFS over time and the median duration of PFS. Patients with no PFS event will be censored at the date of their last disease assessment.

Time to next therapy is defined as the time from the initial administration of Daratumumab, Clarithromycin, Pomalidomide, and Dexamethasone on trial to next treatment.

OS is defined as the time from the initial administration of Daratumumab, Clarithromycin Pomalidomide and Dexamethasone to death from any cause. Kaplan-Meier methods will be used to estimate the OS function. Patients who do not die will be censored at the date that the patient was last known to be alive.

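### The ±17.9% precision stated for the primary ≥VGPR proportion does not fit 40 patients; the exact 95% interval at the expected 25% is 12.7% to 41.2%

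*Combined protocol and SAP*

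**What the plan says.** Section 8.1 (Statistical Methods) follows its power and type I error statements with a precision statement. It begins "A 95% confidence interval constructed around the expected" and continues that the "VGPR response proportion of 25% can be estimated to be within $\pm$ 17.9% of the observed" proportion.

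The sample size is the same wherever it appears. The Protocol Summary says "This study will enroll 40 subjects and screen up to 44 subjects"; Section 4.2 says "Approximately 40 patients will be enrolled and treated on study"; and Section 8.1.1 counts responders "among the 40 patients entered into the cohort", with success at 8 or more. The design parameters are also in Section 8.1.1: "The sample size computations were performed assuming a 5% level of significance and 80% power", a null "VGPR response proportion of 9%, below which the regimen will be unacceptable", and a target of 25%.

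On method, Section 8.1 and the Endpoints entry of the Protocol Summary say only that the primary interval rests on binomial proportions. Section 8.1.6, under Response, is specific for the best-response categories: "A two-sided 95% exact binominal CI will be calculated for each category".

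**The concern.** Everything needed to calculate the half-width is fixed in the plan: a proportion of 25%, 95% confidence and 40 patients. The printed 17.9 points is visibly too large for those inputs, and it is the only statement of how precisely the primary endpoint will be estimated.

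It also conflicts with the sentences around it. Read as the interval at the expected result, 25% ± 17.9 runs from 7.1% to 42.9% and includes the 9% null. A reader would conclude that a trial performing exactly as hoped could not exclude the null rate, although the same paragraph claims at least 80% probability of a positive result at 25%. One of the two statements has to be wrong, and the reader cannot tell which without redoing the calculation.

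**Working it through.** **Inputs**

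- Patients: n = 40 (Protocol Summary, Sections 4.2 and 8.1.1).
- Expected proportion: p = 0.25, which is 10 of 40 (Section 8.1).
- Confidence level: 95%, z = 1.96 (Section 8.1).
- Null proportion: 0.09; success at 8 or more responders (Section 8.1.1).

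**Step 1. The design statements reproduce.** With X the number of responders among 40:

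- P(X ≥ 8 | p = 0.09) = 0.0242, so the probability of a negative result at 9% is 1 − 0.0242 = 0.976. The plan claims at least 0.95.
- P(X ≥ 8 | p = 0.25) = 0.818. The plan claims at least 0.80.

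**Step 2. The precision figure does not.** The normal-approximation (Wald) half-width is

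1.96 × √(p(1 − p)/n) = 1.96 × √(0.25 × 0.75/40) = 0.134,

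giving 11.6% to 38.4%. Other 95% methods at 10/40:

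| Method | Half-width (points) | Interval |
|---|---|---|
| Wald | 13.4 | 11.6% to 38.4% |
| Wald, continuity-corrected | 14.7 | 10.3% to 39.7% |
| Wilson | 13.0 | 14.2% to 40.2% |
| Agresti-Coull | 13.2 | 14.0% to 40.4% |
| Jeffreys | 13.1 | 13.6% to 39.8% |
| Exact (Clopper-Pearson) | 14.3 | 12.7% to 41.2% |

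The exact interval is asymmetric: 25.0 − 12.7 = 12.3 points below and 41.2 − 25.0 = 16.2 points above.

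**Step 3. No other response rate rescues it.** At n = 40 the Wald half-width is largest at p = 0.5, where 1.96 × √(0.25/40) = 0.155. The longest single arm of the exact interval, over every count from 0 to 40, is 16.7 points. Both are below 17.9. Raising the confidence level to 99% does not reproduce the figure either: at 25% it gives 17.6 (Wald) or 18.1 (exact).

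**Step 4. What would give 17.9.**

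- At p = 0.25: n = 1.96² × 0.25 × 0.75/0.179² ≈ 22.5.
- At p = 0.50: 1.96 × √(0.25/30) = 0.179, so n = 30.

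Neither sample size appears in the documents. The match at n = 30 suggests a figure carried over from another calculation, but that is inference and the finding does not depend on it.

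**Step 5. The corrected precision agrees with the decision rule.** The exact 95% interval is 9.05% to 35.6% at 8/40 and 7.3% to 32.8% at 7/40. The lower limit therefore passes 9% at exactly the count the plan sets for success. At the expected 10/40 it is 12.7%, well clear of the null.

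**The case against.** The best defence is the word *within*. Read literally, the sentence gives an upper bound, and the bound is true: every 95% interval tried at 10/40, including the longer exact arm of 16.2 points, is shorter than 17.9. On that reading the sentence is loose and errs on the cautious side. It does not strictly contradict the power claim, because power rests on the count of 8 of 40 and not on a planning interval. It also cannot contaminate the results, since the reported interval will be calculated from the data.

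Much of this stands. The sample size, decision rule, type I error, power and planned analysis are untouched. It is also fair that the size of the discrepancy depends on the comparison. The excess is 17.9 − 13.4 = 4.5 points (about a third) against Wald, but 17.9 − 14.3 = 3.6 points (about a quarter) against the exact half-width and 17.9 − 16.2 = 1.7 points against the longer exact arm.

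The upper-bound reading itself does not persuade. The sentence ties a figure with one decimal place to a specific proportion of 25%, which is how a calculated half-width is reported. A bound wider than the worst case over all response rates tells the reader nothing about this trial.

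Patients dropping out of the full analysis set (Section 8.1.3.2) do not explain it either: the denominator would have to fall from 40 to 22 or 23.

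**Conclusion.** The concern holds. The ±17.9% is not the precision of a 40-patient design at a 25% response proportion under any standard 95% method. The correct statement is 12.7% to 41.2% by the exact method, or ±13.4 points by the normal approximation. The half-width is overstated by 3.6 to 4.5 points depending on which of these is taken as the reference, and the lower limit at the expected result is 12.7% (exact) or 11.6% (Wald), not 7.1%.

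This assumes all 40 patients are in the denominator and that the expected result is 10 responders. The fault is confined to the precision sentence; the power and type I error statements beside it are correct. Because the error understates precision and drives no decision, it should be corrected but does not threaten the design.

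**What to change.** Replace the precision sentence in Section 8.1 with: *With 40 patients and an observed ≥VGPR proportion of 25% (10/40), the exact two-sided 95% confidence interval is 12.7% to 41.2%.* Giving the limits avoids a symmetric ± for an asymmetric interval.

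As an optional clarification, name the exact (Clopper-Pearson) method for the primary endpoint, to match what Section 8.1.6 already sets for the response categories. That wording occurs in Section 8.1 and in the Endpoints entry of the Protocol Summary, and both should change together.

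The cost is one sentence for the correction and two short edits for the clarification. Nothing changes in the sample size, the 8-of-40 rule or trial conduct.

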#### 8.1.1 Determination of Sample Size

The sample size computations were performed assuming a 5% level of significance and 80% power. The new regimen will be declared effective and worthy of further testing if 8 or more patients have  $\geq$  VGPR among the 40 patients entered into the cohort.

Sample size recommendations for the current design are determined according to A'Hern's exact single-stage phase II design (A'Hern, RP, 2001). We project a  $\geq$  VGPR response proportion of 9%, below which the regimen will be unacceptable, and a  $\geq$  VGPR response proportion of 25%, above which the regimen will be considered worthy of further exploration. The null hypothesis that the  $\geq$  VGPR response proportion is less than or equal to 9% will be tested against the alternative hypothesis that the  $\geq$  VGPR response proportion is greater than or equal to 25%.

#### 8.1.2 Randomization and Stratification

There is no randomization or stratification of this study.

### 8.1.3 Populations for Analysis

#### 8.1.3.1 Enrolled Analysis Set

The enrolled analysis set will include all patients who signed an ICF and were enrolled.

#### 8.1.3.2 Full Analysis Set

The full analysis set will include all patients enrolled on the study who received any amount of Daratumumab, Clarithromycin, Pomalidomide, and Dexamethasone and who had at least 1 post-baseline disease assessment.

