#### 8.1.6 Efficacy Analysis

Efficacy analysis will be performed for all patients enrolled on the study in the full analysis set.

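### The efficacy set leaves out patients with no post-baseline assessment, so early deaths and losses drop from the response rates, PFS and OS, although the decision rule counts all 40 entered

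*Combined protocol and SAP*

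**What the plan says.** Section 8.1.3.2 sets two conditions for the full analysis set beyond enrolment: some exposure to daratumumab, clarithromycin, pomalidomide and dexamethasone, "and who had at least 1 post-baseline disease assessment". Section 8.1.6 then states: "Efficacy analysis will be performed for all patients enrolled on the study in the full analysis set".

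Section 8.1.1 puts the decision on a different footing. The regimen is declared effective if 8 or more patients reach VGPR or better "among the 40 patients entered into the cohort".

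Section 8.1.6 starts PFS and OS at first administration and counts death from any cause as an event in both.

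Three other places could have settled the matter but do not:
- Section 8.1.3.1 defines an enrolled analysis set, but no analysis is assigned to it.
- Section 8.1 describes the primary proportion and its 95% interval without naming a population.
- Section 8.1.4 covers missing data for time-to-event and quantitative endpoints. It does not say how to classify a patient who has no response assessment.

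**The concern.** Reaching a first disease assessment is itself partly an outcome. A patient who dies, withdraws consent or is lost before it cannot be a responder, and under the full analysis set is not counted as a failure either. All such exclusions push the response rates the same way, upward.

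For PFS and OS the conflict is internal. The endpoint definitions count a death in the first weeks as an event, but the population definition removes the patient who had it.

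The trial has no control arm, and Section 4.1 judges it against historical pomalidomide/dexamethasone. The pomalidomide/dexamethasone tables in Section 1.4.2 use denominators of 113 in Trial 1 and 302 and 153 in Trial 2, against safety populations of 112, 300 and 150. Those results are therefore on denominators at least as large as the treated population. The population behind the 9% benchmark is not stated. A rate conditioned on assessment would not be like for like with results that count everyone.

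**Working it through.** **Inputs.** From Section 8.1.1: n = 40, cutoff r = 8, null rate 9% ("response proportion of 9%, below which the regimen will be unacceptable"), target 25% ("response proportion of 25%, above which the regimen will be considered worthy of further exploration"), 5% significance and 80% power. The test is one-sided by construction. The number excluded, d, is not in the documents. I assume d = 1 to 4 and that none of the excluded patients is a responder.

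**Step 1: reproduce the plan's rule.** With X binomial(40, p):
- Type I error = P(X ≥ 8 | 40, 0.09) = 0.024, within the stated 0.05.
- Power = P(X ≥ 8 | 40, 0.25) = 0.818, above the stated 0.80.

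The rule works as claimed with all 40 entered patients counted.

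**Step 2: does the decision change?** Removing d patients without a response takes nothing from the numerator. The number of responders is the same among 40 or among 40 − d, so whether it reaches 8 is the same. With the cutoff held at 8, the decision and its error rates for the 40 entered patients are unaffected.

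**Step 3: does the reported estimate change?** The proportion is 8/(40 − d). The exact (Clopper-Pearson) limits for x responders in n are the 2.5% quantile of Beta(x, n − x + 1) and the 97.5% quantile of Beta(x + 1, n − x). With x = 8:

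| Excluded d | Set size n | 8/n | Exact 95% CI | 40/n |
|---|---|---|---|---|
| 0 | 40 | 20.0% | 9.05% to 35.65% | 1.000 |
| 1 | 39 | 20.5% | 9.30% to 36.46% | 1.026 |
| 2 | 38 | 21.1% | 9.55% to 37.32% | 1.053 |
| 3 | 37 | 21.6% | 9.83% to 38.21% | 1.081 |
| 4 | 36 | 22.2% | 10.12% to 39.15% | 1.111 |

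The last column is the factor by which any response proportion rises (VGPR or better, ORR, CR or better, MRD negativity), provided its denominator is the full analysis set.

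**Step 4: does the interval's relation to 9% change?** With 8 responders the lower limit is above 9% at every n from 40 to 36. With 7 responders it runs from 7.34% (n = 40) to 8.19% (n = 36), below 9% throughout. In neither case does the reading against 9% flip.

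**Step 5: PFS and OS.** If the d excluded patients all died early and there is no censoring before time t, the estimate at t is S/(40 − d) instead of S/40, where S is the number event-free. The same factor applies: 1.026 to 1.111. Excluded patients who were lost or withdrew, and did not die, would have been censored very early, and removing them changes the Kaplan-Meier curve little.

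**The case against.** The strongest case against is that the primary decision is already protected. Section 8.1.1 fixes 8 responders among 40 entered, and step 2 confirms that dropping non-responders cannot alter it. That stands. The shift in the estimate, 0.5 to 2.2 percentage points, is also small beside an interval more than 26 points wide. Deaths are not hidden either: Section 9.1.2 makes every death an SAE, Section 8.1.5 lists deaths, and the stopping rule in Section 8.1.7 counts them without reference to this set. These facts limit the consequence. They do not remove the conflict in the efficacy analyses.

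A reader might infer more than the documents support:

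- **That type I error is inflated.** If the cutoff were re-derived for a set of 37 or fewer it would fall to 7. With a true rate of 9% among the 40 entered, the type I error would then be about 0.063. No section provides for a re-derived cutoff.
- **That excluded patients are replaced, up to 44 entered.** The 44 in the Protocol Summary is a screening ceiling, and no replacement rule exists.
- **That early progressors leave the set.** Documented progression normally rests on a post-baseline assessment, so these patients generally stay in.
- **That early toxicity is removed in general.** The schedule has myeloma laboratory tests every cycle and again at the End of Treatment visit (Section 7.3). A patient who stops early for toxicity usually still qualifies, unless death, withdrawal of consent or loss comes first.
- **That the four-drug condition excludes many.** It asks only for any amount of each drug, and all four start in Cycle 1. Missing some doses does not exclude anyone.

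The absence of a named safety set is a separate point of missing detail.

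**Conclusion.** The concern holds in a limited form, and the plan should be corrected before the primary analysis. As written, patients who die, withdraw or are lost before a first assessment, and the few who never start one drug, drop out of the efficacy analyses. This conflicts with the denominator in Section 8.1.1 and with the PFS and OS definitions in Section 8.1.6.

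The go/no-go decision does not change while the cutoff stays at 8 responders. The effect is an upward bias in the reported VGPR-or-better, ORR, CR and MRD-negativity rates and their intervals, and in PFS and OS. At 8 responders it amounts to 20.5% to 22.2% instead of 20.0%, with a lower limit of 9.3% to 10.1% instead of 9.05%.

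Those figures rest on the assumed 1 to 4 exclusions. The background data do not settle the number. Section 1.1 reports no grade 5 events and 3% discontinuation with clarithromycin, pomalidomide and dexamethasone. Section 1.3.2.2 reports 9 deaths among 103 patients on daratumumab, pomalidomide and dexamethasone, but over the whole treatment period plus 30 days. Neither says how many losses came before a first assessment. If nobody is excluded, there is no bias.

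**What to change.** In Sections 8.1.3 and 8.1.6:

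1. Define the primary efficacy set as all enrolled patients who received any dose of any study drug, with no post-baseline requirement.
2. Count patients without a response assessment as non-responders for VGPR or better, ORR, CR or better and MRD negativity.
3. Keep these patients in PFS and OS from first dose.
4. State that the 8-of-40 rule and the primary confidence interval use this set, and that the cutoff stays at 8 responders and is not re-derived for a smaller set.
5. Keep the present full analysis set as a response-evaluable sensitivity analysis.

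The cost is a wording change to the protocol or SAP, with no new data and no change in sample size. The downside is that reported response rates may be slightly lower.
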